4.3.2. Secondary & Tertiary Endpoints

Measures of immunogenicity will include, where practicable:

Ex vivo ELISPOT responses to overlapping pools of ME-TRAP peptides Cultured ELISOPT responses to overlapping pools of ME-TRAP peptides ICS by flow cytometry TRAP antibody ELISA

VAC 041 Protocol: Version 6.0

Although not a safety or immunogenicity endpoint, neutralising antibody titre against AdCh63 will be measured to establish if high-titre neutralising antibodies against the AdCh63 vector correlate with measures of immunogenicity.

Although not a safety or immunogenicity endpoint, polymerase chain reaction (PCR) testing for *Plasmodium falciparum* will be performed on blood taken at the first vaccination visit to facilitate interpretation of immunogenicity data in the context of possible natural exposure to malaria. This PCR assay for *P. falciparum* is still under development and is not validated for clinical diagnostic purposes.

As a tertiary endpoint, a comparison of the immunogenicity of two doses of MVA ME-TRAP will be made.

4.4. Safety

4.4.1. Safety Monitoring

Safety oversight will be the responsibility of the investigators, the independent Local Safety Monitor (LSM) and the independent Data Safety and Monitoring Board (DSMB).

Safety monitoring for Group 1

[figure not shown]
The dose escalation of AdCh63 ME-TRAP to 5 x 10¹⁰vp between groups 1A and 1B will only occur following satisfactory safety review by the DSMB.

Safety monitoring for Groups 2 and 3

As detailed in the schedule below, administration of AdCh63 ME-TRAP will occur in three stages. Approval from the Chair of the Gambia Government/MRC Laboratories Ethics Committee and DSM following submission of 14-day safety profiles following stage 1a will be required to proceed to stage 2a. Approval from the Chair of the Gambia Government/MRC Joint Ethics Committee following submission of 14-day safety profiles to the DSMB following stage 2a will be required to proceed to stage 3a.

Stage 1a		Group 2A Group 2C	AdCh63 ME-TRAP 1 x 10 HDCRV 1ml IM	¹⁰ vp IM
Stage 2a		Ļ	 Submission of 14 day safe Ethics Committee Approval from the Chair of DSMB 	ety profile to DSMB & Chair of
J	Group 2BAdCh63 ME-TRAP 1 x 1010 vp IMGroup 3AAdCh63 ME-TRAP 5 x 1010 vp IM			
Stage 3a		Ļ	 Submission of 14 day safet Approval from the Chair of DSMB 	i i
	Group 3B Group 3C		53 ME-TRAP 5 x 10 ¹⁰ vp IM V 1ml IM	

As detailed in the schedule below, administration of MVA ME-TRAP will occur in three stages. Approval from the Chair of the Ethics Committee & DSMB following submission of 14-day safety profiles to the DSMB & Ethics Committee following stage 1b will be required to proceed to stage 2b. Approval from the Chair of the Ethics Committee & DSMB following submission of 14-day safety profiles to the DSMB & Ethics Committee following submission of 14-day safety profiles to the DSMB & Ethics Committee following submission of 14-day safety profiles to the DSMB & Ethics Committee following submission of 14-day safety profiles to the DSMB & Ethics Committee following stage 2b will be required to proceed to stage 3b.

4.4.2. Discontinuation of the Study

Both arms of the study will be discontinued in the event of any of the following:

- New scientific information is published to indicate that volunteers in the study are being exposed to undue risks as a result of administration of the IMPs by any route of administration, or as a result of the follow-up schedule.
- Serious concerns about the safety of the IMPs arise as a result of one or more vaccine related SAE occurring in the subjects enrolled in this or any other ongoing study of the IMPs.
- For any other reason at the discretion of the Principal Investigator.

4.5. Data Collection

Adverse events will be documented in individual case report forms (CRFs) for each volunteer. They will be recorded under two headings; local and general. There will be separate sections for concomitant medication, concomitant vaccination, non-serious adverse event documentation, serious adverse event documentation and study conclusion. Any deviations from the study protocol will be documented (see section 12.6). Case report forms will be kept securely, and HIV status will not be recorded in the CRF.

5. SELECTION AND WITHDRAWAL OF SUBJECTS

5.1. Inclusion Criteria

Consenting adult males aged 18-50 years in good health and healthy children aged 2-6 years.with consenting parents.

5.2. Exclusion Criteria

Any of the following constitute an exclusion criterion:

- Clinically significant history of skin disorder (psoriasis, contact dermatitis etc.), allergy, symptomatic immunodeficiency, cardiovascular disease, respiratory disease, endocrine disorder, liver disease, renal disease, gastrointestinal disease, neurological illness.
- Severe malnutrition.
- Hypersensitivity to HDCRV.
- History of allergic disease or reactions likely to be exacerbated by any component of the vaccines, e.g. egg products, Kathon, neomycin, betapropiolactone.
- History of splenectomy
- Haemoglobin less than 9.0 g/dL, where judged to be clinically significant in the opinion of the investigator
- Serum Creatinine concentration greater than 70 μmol/L, where judged to be clinically significant in the opinion of the investigator
- Serum ALT concentration greater than 45 U/L, where judged to be clinically significant in the opinion of the investigator
- Blood transfusion within one month of enrolment.
- History of vaccination with previous experimental malaria vaccines.
- Administration of any other vaccine or immunoglobulin within two weeks before vaccination.
- Current participation in another clinical trial, or within 12 weeks of this study.
- Any other finding which in the opinion of the investigators would increase the risk of an adverse outcome from participation in the trial.
- Likelihood of travel away from the study area.
- HIV positive.
- Positive malaria antigen test

5.3. Withdrawal Criteria

Subjects may be withdrawn from the study:

- By withdrawing consent
- On the decision of the Investigator
- On the advice of the DSMB

The Investigator may withdraw the subject for any of the following reasons:

- Any adverse event which results in inability to comply with study procedures
- Ineligibility either arising during the study or retrospectively (having been overlooked at screening)
- Significant protocol deviation

• Loss to follow up (applies to a subject who consistently does not return for protocol study visits, is not reachable by telephone or other means of communication and/or is not able to be located)

The reason for withdrawal will be recorded in the CRF. If the subject is withdrawn due to an AE, the Principal Investigator will arrange for appropriate specialist management or follow up visits until the AE has resolved or stabilised. The regulatory authorities will be informed in a timely manner according to recognised guidelines. The extent of follow up after premature discontinuation will be determined by the Investigator but will be at least for the whole study period. If possible within the study period, volunteers will be replaced.

6. RANDOMISATION

Adult volunteers in group 1 will be allocated to study groups by investigators (i.e. not randomised). Children in groups 2 and 3 will be randomised to groups A, B or C. Randomisation of subjects will done by an independent statistician at the Centre for Statistics in Medicine, Oxford using stratified randomisation (stratified on age - 2 categories, split by the median value of those recruited). As all volunteers will be recruited and screened before randomisation, the allocation list will be prepared after the final patient has been screened. The statistician carrying out the randomisation will have no knowledge of the participants, with the exception of age, as this is required for the stratification.

7. BLINDING

For groups 2 and 3, the investigators and the vaccinators will be un-blinded to the group allocations. However, the children's parents/carers and field worker assessing adverse events in the 3 days immediately following vaccination will be blinded to the group allocation.

8. INVESTIGATIONAL MEDICINAL PRODUCT

8.1. Description

MVA ME-TRAP is manufactured under Good Manufacturing Practice conditions by Impfstoffwerk Dessau-Tornau (IDT), Germany. MVA ME-TRAP is supplied as a liquid. The vaccine suspension is supplied as sterile 0.2 mL aliquots in 1.0 mL clear glass injection vials.

AdCh63 ME-TRAP is manufactured under Good Manufacturing Practice conditions by the Clinical Biomanufacturing Facility (CBF), Churchill Hospital, Oxford. The virus suspension is supplied as sterile 0.6 mL aliquots in glass vials.

HDCRV is manufactured by Sanofi Pasteur MSD Ltd. It is supplied as a dry pinkish beige to orangey yellow dry powder for reconstitution in a solvent (water for injection, a clear, colourless solution).

8.2. Formulation

MVA ME-TRAP will be provided in lots of vials of 200 μ L or 450 μ L volume in 10 mM Tris buffer. The dose of MVA ME-TRAP to be used in this study is 1 or 2 × 10⁸ pfu.

Each vial of AdCh63 ME-TRAP contains a concentration of 1.35×10^{11} vp/ml in 10 mM Histidene, 35 mM NaCl. The doses of AdCh63 ME-TRAP to be used in this study will be 1×10^{10} vp (Groups 1A, 2A & 2B) and 5×10^{10} vp (Groups 1B, 2B, 3A & 3B).

After reconstitution the HDCRV is 1ml, (inactivated, strain PM/WI 38 1503-3M) \geq 2.5 IU. Excipients are human albumin solution and water for injection (1ml). The dose will be 1ml.

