We will examine the safety and immunogenicity of the vaccination regimen found to be protective in Oxford (i.e. AdCh63 ME-TRAP prime followed by MVA ME-TRAP boost). MVA ME-TRAP has been extensively used in clinical trials (including sites in Kenya and The Gambia), and so we propose to begin with the full dose. AdCh63 ME-TRAP has not been used before in The Gambia, and so we propose to begin with one fifth of the dose used in Oxford in 6 volunteers before increasing to the full dose. AdCh63 ME-TRAP has previously been delivered by intramuscular (IM) injection and MVA ME-TRAP has usually been given by intradermal (ID) injection. However, MVA can be safely delivered by the intramuscular route [55] and IM MVA ME-TRAP is under review in Oxford. As IM would be the preferred route of administration for vaccinations in children, we propose to administer all vaccines by the IM route.

We do not propose to include a placebo group for adult volunteers. At this stage our objective is to describe the safety profile in a small number of individuals, and the confidence intervals for the proportion of individuals with a particular event would be too wide for meaningful comparison with a placebo group. Immunogenicity will be judged by comparison with baseline.

GROUPS 2&3:

Following analysis of data from group 1, in the event of:

- 1. Acceptable safety and tolerability (ie demonstration of a similar adverse event and safety profile to that seen in healthy adult volunteers to date and favourable review by the DSMB) and
- 2. Acceptable immunogenicity (a mean of ≥ than 500 antigen specific SFU/million PBMCs observed post boost)

we will plan to subsequently assess safety and immunogenicity in 24 healthy children aged 2-6 years (Groups 2-3) compared to 12 healthy controls (aged 2-6 years). AdCh63 ME-TRAP has not been administered to children before, and so we propose to begin with one fifth of the dose used in Oxford in adult volunteers (group 2) before increasing to the full dose of AdCh63 ME-TRAP (group 3). It is anticipated that the full dose of 5 x 10¹⁰ vp AdCh63 ME-TRAP will be tolerated in children aged 2-6.

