4.2. Study groups

Study groups are as follows: (All injections are administered by the intramuscular route – IM).

Group 1A (6 healthy male volunteers aged 18-50 years): AdCh63 ME-TRAP 1 x 10^{10} vp IM followed by MVA ME-TRAP 2 x 10^{8} pfu IM 8 weeks later

Group 1B (10 healthy male volunteers aged 18-50 years): AdCh63 ME-TRAP 5 x 10¹⁰ vp IM followed by MVA ME-TRAP 2 x 10⁸ pfu IM 8 weeks later

Group 2A (6 healthy children aged 2-6 years): AdCh63 ME-TRAP 1×10^{10} vp IM followed by MVA ME-TRAP 1×10^{8} pfu IM 8 weeks later

Group 2B (6 healthy children aged 2-6 years): AdCh63 ME-TRAP 1 x 10¹⁰vp IM followed by MVA ME-TRAP 2 x 10⁸ pfu IM 8 weeks later

Group 2C (6 healthy children aged 2-6 years): Control HDCRV 1ml IM followed by HDCRV 1ml IM 8 weeks later

Group 3A (6 healthy children aged 2-6 years): AdCh63 ME-TRAP 5 x 10^{10} vp IM followed by MVA ME-TRAP 1 x 10^{8} pfu IM 8 weeks later

Group 3B (6 healthy children aged 2-6 years): AdCh63 ME-TRAP 5 x 10^{10} vp IM followed by MVA ME-TRAP 2 x 10^{8} pfu IM 8 weeks later

Group 3C (6 healthy children aged 2-6 years): Control HDCRV 1ml IM followed by HDCRV 1ml IM 8 weeks later

Duration of study involvement, clinic visits and blood sampling regimes are identical for all volunteers in each study group. There will be a total of 7 clinic attendances, 7 blood sampling occasions and two vaccination visits for each volunteer. Total blood volume for the study period (300 days from first vaccination for all volunteers) will be 190 mLs for group 1 and 35mls for groups 2 & 3.

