8.5. Trial Regimen

There will be an initial dose escalation in adults and children to confirm safety of a lower dose of AdCh63 ME-TRAP before using the full dose.

Group 1:

[figure not shown]
Volunteers in group 1B will not be vaccinated until a minimum of 14 days have elapsed following vaccination of volunteers in group 1A, following safety review by the LSM and DSMB.

To avoid a previously unsuspected AE affecting multiple volunteers, one volunteer in group 1A will be vaccinated alone. 48 hours later a further two volunteers will be vaccinated. This is to allow safety assessment by Investigators. In the absence of significant safety concerns affecting these initial volunteers at 48 hours post-vaccination, the remaining volunteers in this group will be vaccinated.

Groups 2 and 3:

Vaccination of volunteers in groups 2 & 3 will not begin until a minimum of 14 days have elapsed following vaccination of volunteers in group 1B, and a safety review of adverse event data for groups 1A & 1B has been reviewed by the LSM & DSMB.

The following flow chart outlines the regimen for vaccination of volunteers in groups 2 and 3.

In stage 1a, two volunteers from group 2A and one control volunteer from group 2C will be immunised simultaneously, with AdCh63 ME-TRAP 1 x 10¹⁰ vp and HDCRV, respectively. The remaining volunteers in groups 2A and 2C will be vaccinated after 48 hours have elapsed, providing there are no safety concerns affecting these initial volunteers.

Stage 2a will not proceed until approval is granted following 14 day safety monitoring following stage 1a. One volunteer from group 2B and two volunteers from group 3A will be immunised simultaneously, with AdCh63 ME-TRAP 1 x 10¹⁰ vp and AdCh63 ME-TRAP 5 x 10¹⁰ vp, respectively. The remaining volunteers in groups 2B and 3A will be vaccinated after 48 hours have elapsed, providing there are no safety concerns affecting these initial volunteers.

Stage 3a will not proceed until approval is granted following 14 day safety monitoring following stage 2a. All volunteers in groups 3B and 3C may be vaccinated simultaneously.

In stage 1b, two volunteers from group 2A and one control volunteer from group 2C will be immunised simultaneously, with MVA ME-TRAP 1 x 10^8 pfu and HDCRV, respectively. The remaining volunteers in groups 2A and 2C will be vaccinated after 48 hours have elapsed, providing there are no safety concerns affecting these initial volunteers.

[figure not shown]

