Stage 2b will not proceed until approval is granted following 14 day safety monitoring following stage 1b. One volunteer from group 2B and two volunteers from group 3A will be immunised simultaneously, with MVA ME-TRAP 2 x 10^8 pfu and MVA ME-TRAP 1 x 10^8 pfu, respectively. The remaining volunteers in groups 2B and 3A will be vaccinated after 48 hours have elapsed, providing there are no safety concerns affecting these initial volunteers.

Stage 3b will not proceed until approval is granted following 14 day safety monitoring following stage 2b. All volunteers in groups 3B and 3C may be vaccinated simultaneously.

Results of the FBC, creatinine and ALT will be reviewed before any immunisation is administered. Results of blood tests will be communicated to volunteers/their carers on their next clinic visit.

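### Protocol section 8.2 lists Group 2B under both AdCh63 ME-TRAP doses, although every other section that states its dose gives 1 x 10^10 vp

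*Protocol*

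**What the plan says.** Section 8.2 of the protocol gives the AdCh63 ME-TRAP concentration, 1.35 x 10^11 vp/mL, and then the two doses with the groups that receive each. The 1 x 10^10 vp dose is for "Groups 1A, 2A & 2B". The 5 x 10^10 vp dose is for "Groups 1B, 2B, 3A & 3B". Group 2B is in both lists.

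The other sections that state an AdCh63 dose for this group agree with one another:

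- The schematic in section 1 gives row B of Group 2 a prime of 1 x 10^10 vp and a boost of 2 x 10^8 pfu.
- Section 2.2 sets out the paediatric escalation as "one fifth of the dose used in Oxford in adult volunteers (group 2) before increasing to the full dose of AdCh63 ME-TRAP (group 3").
- Section 4.2 defines the arm as "Group 2B (6 healthy children aged 2-6 years): AdCh63 ME-TRAP 1 x 10¹⁰vp IM".
- The stage 2a table in section 4.4.1 gives 2B 1 x 10^10 vp and 3A 5 x 10^10 vp.
- Section 8.5 describes the start of stage 2a: "One volunteer from group 2B and two volunteers from group 3A will be immunised simultaneously, with AdCh63 ME-TRAP 1 x 10¹⁰ vp" for 2B, and 5 x 10^10 vp for 3A.

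**The concern.** A single arm cannot have two priming doses, and the contradiction is in current protocol text, not in a change log. Section 8.2 is the investigational product section and the only one in the text shown that gives the AdCh63 concentration. Anyone working out a volume to draw up would therefore go there.

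The setting makes the slip more than cosmetic. Section 2.2 says this vaccine had not been given to children before, and the escalation rests on keeping group 2 at the low prime and group 3 at the full prime. Groups 2B and 3A are primed in the same stage, with their first volunteers vaccinated together at different doses. If the second listing were followed, 2B would have the same regimen as 3B, and no child would receive the low prime with the full boost. Six children would then receive that full-dose combination before the review that must precede the boost in 3B: "Stage 3b will not proceed until approval is granted following 14 day safety monitoring following stage 2b".

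**Working it through.** **Inputs.** Group sizes (section 12.2): 1A has 6, 1B has 10, and each of 2A, 2B, 2C, 3A, 3B and 3C has 6. Concentration (section 8.2): 1.35 x 10^11 vp/mL. Vial (section 8.1): "The virus suspension is supplied as sterile 0.6 mL aliquots in glass vials". Staging: sections 4.4.1 and 8.5.

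**1. Head count from section 8.2 as written.**
- 1 x 10^10 vp: 6 (1A) + 6 (2A) + 6 (2B) = 18.
- 5 x 10^10 vp: 10 (1B) + 6 (2B) + 6 (3A) + 6 (3B) = 28.
- Total listed: 18 + 28 = 46.
- Planned AdCh63 recipients: 16 adults + 24 children (2A, 2B, 3A, 3B; 4 x 6) = 40.
- Excess: 46 - 40 = 6, which is Group 2B counted twice.

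**2. Which entry is wrong.** The count alone cannot decide this, because removing 2B from either list restores 40 (18 + 22, or 12 + 28). The text decides it. Five other places give 2B, or all of group 2, only the lower dose, and none gives it the higher. The correct split is therefore 18 at 1 x 10^10 vp and 10 + 6 + 6 = 22 at 5 x 10^10 vp.

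**3. Size of the discrepancy.**
- Ratio: 5 x 10^10 / 1 x 10^10 = 5.
- Volumes, assuming an undiluted draw (the protocol states no dilution): 1 x 10^10 / 1.35 x 10^11 = 0.074 mL, and 5 x 10^10 / 1.35 x 10^11 = 0.370 mL.
- Vial content: 0.6 mL x 1.35 x 10^11 vp/mL = 8.1 x 10^10 vp. One vial covers either dose, so running short would not reveal a wrong draw.

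**4. Consequence if the second listing were followed.**
- Children given 5 x 10^10 vp before the stage 2a review: planned 6 (3A); otherwise 6 + 6 = 12 (3A and 2B).
- Children given 5 x 10^10 vp and then 2 x 10^8 pfu before the stage 2b review: planned 0, since 3A is boosted with 1 x 10^8 pfu and 3B waits for stage 3b; otherwise 6 (2B).

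**The case against.** The strongest reply is that this is an obvious drafting slip with little practical reach. The right dose comes first in the same sentence. Section 8.2 describes the product, whereas sections 4.2 and 8.5 say who receives what and when, and they are consistent. Section 7 confirms that "the investigators and the vaccinators will be un-blinded to the group allocations". To misdose 2B, staff would have to overlook all of this.

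The staging also limits the harm. In stage 2a only one 2B child and two 3A children are vaccinated first, and the rest follow after 48 hours if there is no safety concern. At that stage 5 x 10^10 vp is already planned for children in 3A. The 2B boost of 2 x 10^8 pfu is as planned either way, and stage 2b still needs approval after stage 1b. The stage 2b review gates only the boost in 3B; its prime is gated by the stage 2a review.

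All of that stands, and it is why misdosing is unlikely. The 48-hour hold would stagger the exposure, but it would not change the number exposed by the time of each review if no concern arose. Nor does any of it remove the contradiction. Several correct statements elsewhere are no reason to leave a wrong paediatric dose assignment in the product section.

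**Conclusion.** The concern holds. Section 8.2 wrongly lists Group 2B at 5 x 10^10 vp; the intended dose is 1 x 10^10 vp, and the rest of the protocol leaves no doubt about it. The error affects the stated dose of six children by a factor of five. It does not touch the group definitions, endpoints or planned sample size. The exposure counts (12 rather than 6, and 6 rather than 0) apply only if the wrong entry were acted on, and the volumes assume an undiluted draw. The error should be corrected because it is a certain mistake in a dose statement within a paediatric dose escalation, even though the chance of harm is low.

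**What to change.** Delete 2B from the second list, so that section 8.2 assigns 1 x 10^10 vp to Groups 1A, 2A and 2B, and 5 x 10^10 vp to Groups 1B, 3A and 3B. As a precaution, check any dose-preparation procedures against the corrected lists before stage 2a. Section 8.4 refers to administration procedures that are not shown, and nothing suggests that they repeat the error. The cost is a one-line correction and a short document check.

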8.3. Product Storage

The AdCh63 ME-TRAP and MVA ME-TRAP vials are stored between -70° C and -90° C, in a locked freezer at the University of Oxford, Churchill Hospital. All movements of the study vaccines between IDT or CBF and the University of Oxford and between the locked freezer and clinic room will be documented. The vaccines will be shipped from Oxford on dry ice, then stored in a -70° C freezer at the MRC unit until required. HDCRV will be stored between $+2^{\circ}$ C and $+8^{\circ}$ C. Records of vaccine storage will be documented in a vaccine accountability log.

8.4. Dispensing and Administration

Malaria vaccines will be transported to Sukuta Health Centre on dry ice on the morning of use. They will be thawed at Sukuta Health Centre and kept in a cold box, and used within 4 hours of thawing. HDCRV will be removed from a refrigerator and kept in a cool-box until used.

The following constitute contraindications to administration of vaccine at that point in time; if any one of these occur at the time scheduled for vaccination, the subject may be vaccinated at a later date, or withdrawn at the discretion of the Principal Investigator. Medical care including inpatient care if necessary will be offered.

- Acute disease at the time of vaccination (Acute disease is defined as the presence of a moderate or severe illness with or without fever) All vaccines can be administered to persons with a minor illness such as mild diarrhoea, mild upper respiratory infection with or without low-grade febrile illness, *i.e.* axillary temperature of <37.5°C (99.5°F). Details of any minor illness will be recorded in the CRF.
- Axillary temperature of \geq 37.5°C (99.5°F) at the time of vaccination.

AdCh63 ME-TRAP and MVA ME-TRAP will be administered intramuscularly according to standard operating procedures (SOP). Each volunteer will be monitored for one hour (or longer if necessary) after each vaccination. Resuscitation (including intubation) equipment and medication will be available in the clinic site and a clinician trained in resuscitation will be present at all times.

AdCh63 ME-TRAP and MVA ME-TRAP are genetically modified organisms. In order to minimise dissemination of the recombinant vectored vaccine viruses into the environment, the inoculation site will be covered with a dressing after immunisation. This should absorb any virus that may leak out through the needle track, and will be removed from the injection site after 30 minutes. Vaccine administrators will follow precautions for the safe handling of GMOs (including the use of eye protection and gloves).

HDCRV 1ml will be administered using an identical type of needle and syringe to those used to administer malaria vaccines. In order to ensure adequate blinding of the volunteer and their carer, the same personal protective equipment will be worn by the vaccinator, as described above.

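### Carer blinding in section 8.4 covers needle, syringe and protective equipment but not injected volume or dressing, which weakens it for carer-reported events

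*Protocol*

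**What the plan says.** Section 7 of the Protocol leaves investigators and vaccinators unblinded in Groups 2 and 3. It blinds the parents or carers, and adds that the "field worker assessing adverse events in the 3 days immediately following vaccination will be blinded to the group allocation". Section 4.1 gives the purpose: to limit bias in adverse event reporting. Section 9.1 says that carers learn which vaccine their child had only when the study ends.

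Section 8.4 sets out how the injection itself is blinded. On equipment it says: "HDCRV 1ml will be administered using an identical type of needle and syringe to those used to administer malaria vaccines". It then has the vaccinator wear the same protective equipment, with the stated aim of blinding the volunteer and carer. It names no other matching measure.

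The dressing appears in the preceding paragraph of section 8.4, on genetically modified organisms. It is there to catch recombinant virus leaking from the needle track and comes off after 30 minutes. The HDCRV paragraph refers back to the protective equipment but not to the dressing.

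On volume, section 8.2 says of HDCRV: "Excipients are human albumin solution and water for injection (1ml). The dose will be 1ml". Neither section 8.2 nor section 8.4 states an injected volume or a diluent for AdCh63 ME-TRAP, or an injected volume for MVA ME-TRAP.

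**The concern.** By matching protective equipment for the carer's benefit, the Protocol accepts that a carer can draw inferences from what happens at the injection. Two other cues are left open: how full the syringe is, and whether a dressing goes on. With the same type of syringe in every arm, a difference in fill is, if anything, easier to notice.

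The primary endpoint (section 4.3.1) is adverse events, and the paediatric control groups exist to help judge objectively whether events are related to vaccination (section 4.1). Several solicited events in children are known only through the carer. Section 11.3.6 treats every local reaction as vaccine-related, so biased reporting of pain would pass straight into the endpoint. The relationship of other events is judged by the investigator, who is unblinded, so blinded reporting carries much of the weight.

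**Working it through.** The Protocol gives no injected AdCh63 volume or volume ratio, so there is no planned figure to reproduce. The check derives volumes from section 8.2.

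**Inputs**
- Concentration (section 8.2): "Each vial of AdCh63 ME-TRAP contains a concentration of 1.35×10^{11} vp/ml".
- Doses (section 8.2): "1×10^{10} vp (Groups 1A, 2A & 2B) and 5×10^{10} vp (Groups 1B, 2B, 3A & 3B".
- Vial fill (section 8.1): "The virus suspension is supplied as sterile 0.6 mL aliquots in glass vials".
- Control volume: 1 mL (section 8.2).
- MVA (section 8.2): "MVA ME-TRAP will be provided in lots of vials of 200 μ L or 450 μ L volume in 10 mM Tris buffer". No pfu/mL is given.

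**AdCh63 prime, assuming no dilution.** Volume = dose ÷ concentration; ratio = 1 mL ÷ volume.
- Lower dose: 1×10^10 ÷ 1.35×10^11 = 0.074 mL; ratio 13.5.
- Higher dose: 5×10^10 ÷ 1.35×10^11 = 0.370 mL; ratio 2.7.
- One vial holds 0.6 × 1.35×10^11 = 8.1×10^10 vp, so either dose can be drawn from a single vial. Undiluted use is therefore feasible, though not stated.

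**Where the contrasts arise.** Under section 8.5, Group 2A and control Group 2C are primed together in stage 1a (13.5-fold), and Groups 3B and 3C in stage 3a (2.7-fold). Stage 2a has no control child, so there is no side-by-side contrast with HDCRV within it.

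**MVA boost.** The volume cannot be derived. Assumed volumes of 0.1, 0.2, 0.45 and 0.9 mL would give ratios of 10, 5, 2.2 and 1.1, so the contrast could be large or negligible.

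**Which endpoint items are exposed.** Table 1 in section 11.2 lists eleven solicited items for children, omitting itch, which is not used in Groups 2 and 3.
- Five rest on the carer's account: pain, reported fever, reduced oral intake, reduced activity and vomiting.
- Six can be seen, felt or measured by the assessor: redness, swelling, warmth, scaling or blistering, limitation of arm movement and documented fever.

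**A side observation.** The dose listing quoted above places Group 2B under both AdCh63 doses, while sections 1, 4.2, 4.4.1 and 8.5 place it under one. These passages must be reconciled. The two ratios stand either way; only which of them applies to Group 2B is affected.

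**The case against.** The best defence is that section 8.4 omits operational detail rather than contradicting anything. It leaves administration of both malaria vaccines to a standard operating procedure that is not shown and may contain dilution or masking steps. A vial concentration is not an injected volume, and no passage says that the carer sees the syringe. Noticing a difference is also not the same as identifying the product: a carer would need to know which volume or dressing belongs to which vaccine, and nothing shows that carers are told.

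These points stand as limits. They do not close the gap, because the Protocol itself sets out its means of blinding the carer, and those means cover neither fill volume nor dressing.

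Some stronger readings are tempting but unsupported:
- *A 13-fold visible difference throughout.* The 13.5 depends on no dilution and applies only to the lower AdCh63 dose. The MVA vial sizes do not establish a contrast at the boost.
- *Control children get no dressing.* The text leaves this unspecified; it does not rule one out.
- *The blinding is lost.* About half the solicited items can be measured by a field worker whose blinding does not depend on what the carer saw. The dressing is off before any home visit, so it is not a cue for that field worker.
- *A calculable bias.* The Protocol gives no reporting rates, and sections 12.1 and 12.5 describe a descriptive study with no formal analysis, so no figure for the bias or its direction can be supported.

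**Conclusion.** The point holds in a limited form. As written, the measures in section 8.4 leave two cues that could let carers see differences between arms: injected volume and the dressing. If AdCh63 is given undiluted, the control volume is 13.5 times larger at the Group 2 prime and 2.7 times larger at the Group 3 prime; at the boost the ratio is unknown. The effect is weaker protection against reporting bias for the five carer-reported solicited items, with the six assessor-observed items less exposed.

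This rests on three assumptions: no dilution, preparation and injection in the carer's view, and a dressing applied only where the containment rationale calls for it. The Protocol neither states nor excludes any of them. The change is worth making even in a descriptive phase I trial, because the paediatric control comparison relies on this blinding and the remedy costs almost nothing.

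**What to change.** Add to section 8.4, for every child and at both vaccinations:
- prepare doses out of the carer's sight;
- cover the syringe barrel with an opaque sleeve or label;
- apply the same dressing, removed at 30 minutes, including for HDCRV recipients.

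No dose or volume should change. Recording carers' guesses of allocation, for example at the last home visit, is an optional check.

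The cost is sleeves or labels, dressings for the 12 control children and a line in the operating procedure. A sleeve hides the fill but not the plunger's travel, so a small cue may remain.
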